## STUDY 2:

## LUNG/OESOPHAGEAL CANCER PATIENTS:

Data from own research shows diaphragm movement of 6.65mm (SD 2.38) (M-mode method). At a power of 0.9 and alpha 0.05, 36 patients are needed (before-after situation) to show a 20% change that is considered clinically relevant. In order to compensate for drop-outs and an unknown diaphragm movement in particular lung surgery patients, it is desired to include 50 patients.

## LVAD/HTX PATIENTS:

A pragmatic approach is desired. It is desired to include all patients who are operated on with the implantation of an LVAD/Heart transplant over 2 years (approx. 40 patients).

## SUMMARY OF DESIRED NUMBER OF INCLUDED PATIENTS

## STUDY 1:

We want 100 patients (34 healthy, 33 pulmonary medicine patients and 33 patients who have had a heart transplant/LVAD) included, distributed equally between the 3 groups to compensate for drop-outs and increase power.

## STUDY 2:

It is desired to include 50 lung/oesophagus patients with the same reasoning as above. Regarding LVAD/heart transplant patients, it is desired to include all patients who are recommended for surgery over 2 years (approx. 40 patients)

#### DATA REGISTRATION

The following demographic data are recorded: sex, height, weight, age and comorbidity. Demographic data is obtained from Region Midt's EPR system as well as anamnestic data. Consent to the trial gives the trial group and any accounting body the right to obtain information in the patient record regarding conditions that are relevant to the trial and for control purposes.

Data is registered in Case-Report-Form in RedCAP, which is administered by Aarhus University. The Danish Data Protection Authority's rules are followed and all personally identifiable data is deleted at the end of the study.

## DATA ANALYSIS

#### STUDY 1:

Movement is measured continuously (centimeters or square centimeters) and calculated as a mean with standard deviation for the various ultrasound measurements. Correlation between diaphragm movement and sex, age, BMI is analyzed with multivariable analysis of variance, MANOVA.

The different measurement methods are compared individually with the golden standard with the paired T-test (Wilcocon's test if non-parametric). The 0 hypothesis is that there is no difference between the index method and the golden standard. Data is also depicted with a Bland-Altman plot and correlation between the index test and the golden standard.

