#### PARTICIPANTS

## STUDY 1:

Participants are divided into 3 categories: 1/3 healthy, 1/3 lung medicine patients and 1/3 patients who have had a heart transplant or LVAD implanted. Everyone over 50 years.

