#### Exclusion criteria:

- Known diaphragm dysfunction
- o Neuromuscular disease
- Pleural effusion. Discovered during the investigation
- o Pneumothorax. Discovered during the investigation
- Healthy group only (1/3): Significant comorbidity affecting heart or lung function (hypertension and mild valvular disease without symptoms is ok), including diagnosed COPD.
- Only healthy group (1/3) and lung disease group (1/3): Previous operation in the thorax

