## ULTRASOUND EXAMINATIONS:

The participants are examined in a standing/sitting position with ultrasound in the mid-axillary line with the liver/spleen as a reference point on the right and left side. A movie clip is saved for later analysis.

Diaphragm movement is measured in 3 different ways: M-mode, Area method and B-mode. [1] [2] [3] [4] Diaphragm thickening fraction is measured in 1 way. [5]

Normal and deep breathing is carried out.

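### Study 1's analysis of diaphragm movement against sex, age and BMI leaves out disease group, so those associations are at risk of confounding by disease

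*Combined protocol and SAP*

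**What the plan says.** The analysis is set out under Data Analysis, Study 1: "Correlation between diaphragm movement and sex, age, BMI is analyzed with multivariable analysis of variance, MANOVA". The sentence before it describes the outcome: "Movement is measured continuously (centimeters or square centimeters) and calculated as a mean with standard deviation for the various ultrasound measurements". Under Ultrasound Examinations there are three movement measures: "Diaphragm movement is measured in 3 different ways: M-mode, Area method and B-mode". The plan does not say which of them enter the MANOVA.

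The sample is built by disease group. The Participants section for Study 1 describes the mix: "Participants are divided into 3 categories: 1/3 healthy, 1/3 lung medicine patients and 1/3 patients who have had a heart transplant or LVAD implanted". The summary of desired numbers gives the sizes: "34 healthy, 33 pulmonary medicine patients and 33 patients who have had a heart transplant/LVAD". Each group is recruited from a different place (day surgery, transplant/LVAD follow-up, lung clinics). The exclusions also differ; the healthy group alone excludes "Significant comorbidity affecting heart or lung function (hypertension and mild valvular disease without symptoms is ok), including diagnosed COPD". The only shared demographic restriction is on age: "Everyone over 50 years".

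Under Data Registration: "The following demographic data are recorded: sex, height, weight, age and comorbidity". Disease group is known for everyone from the inclusion criterion.

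**The concern.** A regression of movement on age, sex and BMI in a sample made of three disease groups mixes two things: how movement varies with age among similar people, and how the groups differ from each other. Without group in the model, the second can pass for the first. This happens when group is related both to the characteristic and to movement.

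Both links are plausible from the protocol itself. The Study 2 background says that an LVAD can restrict the diaphragm and that transplantation can injure the phrenic nerve, so lower movement in the heart group is expected. The groups are recruited separately, with different exclusions and no matching on age, sex or BMI.

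There is a smaller point about the method. The sentence announces an association between movement and each characteristic. A MANOVA test of age asks whether age is related to any of several outcomes jointly. The joint test alone does not say which ultrasound method is affected, in which direction or by how much.

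At stake is the interpretation of a supporting result: an association reported as one of age, sex or BMI could partly reflect the recruitment mix.

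**Working it through.** **The plan's own figure.** None is stated for this analysis, so there is nothing to reproduce. The Study 1 sample size concerns the paired comparison with fluoroscopy.

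**Inputs.** From the plan: groups of 34, 33 and 33 (total 100); predictors sex, age and BMI. Assumed, because the documents give no values: within-group age SD of 8 years; lung group 5 or 10 years older than healthy; heart group the same age as healthy or 5 years younger; movement 0 to 1 within-group SD lower in each disease group; no true age effect; sex and BMI unrelated to group.

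**Expected bias.** Measure age and movement in within-group SDs. Let p be a group's share, a its age shift and m its movement shift. With no true age effect, the expected age slope when group is omitted is approximately b = C/V, where

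- C = Σ(p·a·m) − Σ(p·a)·Σ(p·m)
- V = 1 + Σ(p·a²) − [Σ(p·a)]²

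Lung group 5 years older (5/8 = 0.625 SD), movement 1 SD lower in the lung group only:

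- C = 0.33×0.625×(−1) − (0.33×0.625)×(−0.33) = −0.206 + 0.068 = −0.138
- V = 1 + 0.33×0.391 − 0.206² = 1.086
- b = −0.138/1.086 = −0.127 SD of movement per 8 years of age, where the truth is 0

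Same ages, movement 1 SD lower in both disease groups: C = −0.206 + 0.206×0.66 = −0.070, so b = −0.065, about half.

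Lung group 5 years older, heart group 5 years younger, both 1 SD lower: the product terms cancel and Σ(p·a) = 0, so C = 0 and b = 0.

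**False-positive rate.** Ordinary least squares, 4,000 simulated studies per scenario, two-sided 5% test of age, model without group:

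| Age, lung group | Age, heart group | Movement, lung | Movement, heart | Age falsely significant |
|---|---|---|---|---|
| +5 y | same | −1 SD | same | about 21% |
| +10 y | same | −1 SD | same | about 59% |
| +5 y | same | −1 SD | −0.5 SD | about 15% |
| +5 y | same | −1 SD | −1 SD | about 9% |
| +10 y | same | −1 SD | −1 SD | about 19% |
| +5 y | same | −0.5 SD | −0.5 SD | about 6% |
| +5 y | −5 y | −1 SD | −1 SD | about 4% |
| +5 y | −5 y | −1 SD | same | about 37% |

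When the groups differ in age only, or in movement only (by 0.5 SD), the rate is 5%. With group in the model it is about 5% in every scenario. Simulation error is about ±1 to 2 percentage points. Only age was simulated; the same algebra applies to sex and BMI.

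**Cost in degrees of freedom.** Intercept, age, sex and BMI leave 100 − 4 = 96 residual degrees of freedom; two group indicators leave 100 − 6 = 94.

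**MANOVA.** A model with three outcomes and three continuous predictors was fitted and ran as an ordinary multivariate linear model. Because every outcome has the same predictors, its coefficients for each outcome equal those from separate regressions. The joint test for one predictor has 3 and 94 degrees of freedom and returns a single p-value across the three measures.

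**The case against.** A reader might infer that the coefficients simply are confounded. The documents do not support that. They give no figures for how the groups differ in age, sex, BMI or movement. The age limit and the exclusion of known diaphragm dysfunction in all groups may narrow the differences, though neither matches the groups. Several patterns in the table give essentially no inflation. This objection stands: the supportable claim is risk, and the largest percentages should not be quoted alone. They come from scenarios in which the heart group moves as well as healthy controls, which sits oddly with the protocol's own account of LVAD and transplantation.

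A reader might also infer that MANOVA is the wrong tool. It is not: there are three movement measures, and continuous predictors are allowed. What remains is that the outcome set is undefined, measures in centimetres and square centimetres may be combined, and the joint tests alone do not give the association by method.

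It can be said that an unadjusted correlation in the mixed sample is a legitimate description. That is true, but the mix is fixed by recruitment in thirds, so the result describes no natural population.

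Finally, the impact is small. This analysis is not a listed endpoint, the method comparison is paired within person, and the plan proposes no reference values or adjusted cut-offs that would use these coefficients. All of that stands.

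**Conclusion.** The point holds as a risk of confounding in a supporting analysis. The plan recruits three disease groups in fixed proportions and then relates movement to sex, age and BMI without naming group. Over the assumed patterns examined, the false-positive rate for age runs from about 4% (biases cancel) to about 59% (lung group 10 years older and alone in having lower movement), against about 5% with group included. Those bounds rest on assumed differences and an assumed age SD; they are not predictions for this study. The MANOVA point is one of reporting and specification, not validity. The primary comparison of M-mode with fluoroscopy is unaffected. The priority is low.

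**What to change.** Replace the MANOVA sentence under Data Analysis, Study 1 with: *For each ultrasound method, movement is analysed by linear regression on sex, age, BMI and disease group (three levels); coefficients are reported with 95% CIs.*

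If the sponsor prefers to keep a joint test, the sentence should list the outcomes in it, include disease group, and still report coefficients for each method.

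The cost is one sentence and two residual degrees of freedom (94 in place of 96 at 100 participants). Group is already known from the inclusion criterion, so no new data or participants are needed.

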## BACKGROUND

Shortness of breath is a frequent symptom and can be caused by many different disorders from several different organs. Many patients experience shortness of breath as a result of heart or lung disease or as a complication of thoracic surgery. Shortness of breath is a subjective sensation and can be caused by a lack of oxygen, reduced ventilation or dysfunctional breathing muscles.

The diaphragm is the main breathing muscle. Decreased ability to contract the diaphragm causes shortness of breath. The investigation of dysfunction of the diaphragm is complicated by the fact that newly discovered shortness of breath is not specific to diaphragm dysfunction and can be caused by the many other causes of shortness of breath. Diaphragm dysfunction is therefore an overlooked cause of shortness of breath.

We want to shed more light on the function of the diaphragm. Therefore, we will do two studies. The first is a method study in which different ultrasound methods are compared with the golden standard, x-ray transillumination, in healthy, heart- and lung-diseased patients. The second study will assess the diaphragm function in patients after thoracic surgery (lung surgery and heart transplantation) and in patients where severe heart failure necessitates the need for a mechanical heart heart (Left Ventricular Assist Device, LVAD).

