## STRENGTH CALCULATION

## STUDY 1:

There is no data available for test-retest variance within ultrasound methods or fluoroscopy. It is therefore not possible to make a power calculation of how the spread in the comparison of two methods will be (Limits of agreement with Bland-Altman analysis). The starting point is therefore the bias (absolute difference in mean value) between an ultrasound method (m-mode method) and transillumination. As this is a methodological study, greater requirements are set than in study 2 (see below) for which bias can be detected. Assuming equal variation for the two methods, a detection of bias of 10% (SD 36%, own data for M-mode method) will require 92 participants (power 0.8 and alpha 0.05). Due to uncertainty about SD on the screening method, it is desired to include 100 participants.

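### Study 1 enrols three deliberately different groups but specifies no by-group bias, no by-group limits of agreement and no group term on the method difference

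*Combined protocol and SAP*

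**What the plan says.** All references are to the combined protocol and SAP.

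- **Population.** BACKGROUND describes Study 1 as a method study in which "different ultrasound methods are compared with the golden standard, x-ray transillumination, in healthy, heart- and lung-diseased patients". The participants section sets equal thirds of healthy people, lung patients, and heart transplant or LVAD recipients. The summary of desired numbers fixes the split: "We want 100 patients (34 healthy, 33 pulmonary medicine patients and 33 patients who have had a heart transplant/LVAD) included". The exclusion criteria bar earlier thoracic surgery in the healthy and lung groups only, so the third group differs from the others by design.
- **Sample size.** STRENGTH CALCULATION, Study 1, gives one figure for the whole study: "a detection of bias of 10% (SD 36%, own data for M-mode method) will require 92 participants (power 0.8 and alpha 0.05"). This is raised to 100.
- **Analysis.** DATA ANALYSIS, Study 1: "The different measurement methods are compared individually with the golden standard with the paired T-test", or a Wilcoxon test, with a Bland-Altman plot and a correlation. The Study 1 endpoints section adds only that correlations and Bland-Altman analysis are used where they apply. The MANOVA in the same section relates diaphragm movement to sex, age and BMI.
- **Intended use.** ETHICAL CONSIDERATIONS, Study 1, says that fluoroscopy will not be needed in future for suspected dysfunction, provided correlation and agreement prove good. It makes no distinction by group.

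**The concern.** A single paired test and a single pair of limits summarise agreement well when bias and spread are the same in everyone. The plan recruits three groups that differ in disease and surgical history, and specifies nothing that would show whether that condition holds. The MANOVA does not fill the gap: its outcome is movement rather than the difference between methods, and disease group is not among its factors.

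If the bias differs by group, the pooled mean is a weighted average that may apply to none of them. Positive and negative biases offset each other, and the planned test of no difference will usually be retained. The limits of agreement do not cancel. Between-group bias is added to their width, but the increase is small and carries no information on which group causes it. A general statement that ultrasound can replace fluoroscopy would then rest on an analysis that never looked at the lung or the transplant/LVAD patients separately, although about 33 of each will have been examined.

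**Working it through.** **The plan's own figure.** Inputs: bias 10%, SD 36%, "power 0.8 and alpha 0.05" (taken as two-sided). If 36% is the SD of the paired difference, n = (36 × (1.960 + 0.842) / 10)² = 101.7, so 102, or 104 with the exact t distribution. The stated 92 is not reproduced; 92 gives power 0.75 and 100 gives 0.785. A between-method correlation of about 0.55, or a log-scale calculation, would give about 92, but neither is documented. The present point does not depend on this figure.

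**Inputs for the illustration.**
- Group sizes 34/33/33, from the summary of desired numbers.
- SD of the paired difference within a group: **assumed** 36%. The plan gives 36% as own data for the M-mode method, not as the SD of differences. With the plan's premise, "Assuming equal variation for the two methods", the SD of differences is 36 × √(2(1 − r)) for a between-method correlation r. That is 36% at r = 0.5 and 51% at r = 0. The range shown is 18% to 51%.
- Group biases: **assumed**, for illustration only.

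**Formulas.** With group biases b and sizes n:
- pooled bias m = Σ n·b / 100
- between-group sum of squares B = Σ n(b − m)²
- pooled SD = √(SD² + B/100)
- pooled limits = ±1.96 × pooled SD around m
- one-way test of group: non-central F on 2 and 97 df, λ = B/SD², critical value 3.09

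**Worked case, 0/+15/-15%.** m = (33 × 15 − 33 × 15)/100 = 0. B = 2 × 33 × 225 = 14,850. Pooled SD = √(1296 + 148.5) = 38.0. The limits go from ±70.6 (1.96 × 36) to ±74.5 points. λ = 14,850/1296 = 11.46, giving power 0.86 for the group test. The pooled paired test rejects with probability 0.05 at most, since the pooled SD includes the between-group spread.

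**Worked case, 0/+20/0%.** m = 33 × 20/100 = 6.6%. B = 67 × 6.6² + 33 × 13.4² = 8,844. λ = 6.82.

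**All cases** (power at SD 18% / 36% / 51%):

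| Group biases | Pooled bias | Pooled limits at SD 36% | Power, pooled test | Power, group test |
|---|---|---|---|---|
| 0/+15/-15% | 0 | ±74.5 | at most 0.05 throughout | >0.99 / 0.86 / 0.55 |
| 0/+20/0% | 6.6% | ±72.9 | 0.90 / 0.42 / 0.24 | >0.99 / 0.63 / 0.35 |
| 0/+10/-10% | 0 | ±72.3 | at most 0.05 throughout | 0.98 / 0.50 / 0.27 |
| 0/+10/0% | 3.3% | ±71.2 | 0.42 / 0.15 / 0.10 | 0.63 / 0.19 / 0.12 |

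**What one group of 33 can show.** Power for a 10% bias is 0.87 / 0.34 / 0.19 over the same SDs. For a 20% bias at SD 36% it is 0.87. The 95% CI half-width for bias at SD 36% is 2.037 × 36/√33 = 12.8 points, against 1.984 × 36/√100 = 7.1 points pooled. For each limit of agreement, t × SD × √(1/n + 1.96²/(2(n − 1))) gives 22.0 points at n = 33 and 12.2 at n = 100.

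**The case against.** **The plan does not say that it pools.** Correct. It is silent on group and does not exclude a breakdown. A reader might infer that the sponsor has decided to analyse the 100 only as one sample; the text does not support that. What stands is that one total sample size and one unstratified test per method are all that is specified, so any later split would be post hoc.

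**Separate validation in each group is not a stated aim.** HYPOTHESIS/AIM names no groups, and the reasons given beside the allocation are drop-outs and power. A mixed sample covering a range of users is a fair reading. Even so, BACKGROUND frames the comparison as being in these three populations, and a pooled bias is interpretable for a mixture only if one can see whether it is homogeneous.

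**Opposite biases are speculative.** This stands. No section gives a group-specific bias or a mechanism for one. The Study 1 movement and thickening endpoints are on the right side, whereas the LVAD is described as lying on the left hemidiaphragm. Ultrasound and fluoroscopy are recorded simultaneously, so a true difference in movement between groups does not itself create a method bias. The scenarios show what the analysis could miss, not what is expected.

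**Groups of 33 are too small.** Largely true for hypothesis testing. At the plan's own 10% target and SD 36%, the group test has power 0.19 to 0.50 in the cases shown. Three unadjusted group tests would also carry a familywise error of about 1 − 0.95³ = 14%. This argues for estimates with intervals rather than for leaving groups out.

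**Replacement is conditional.** Also true: the ethics section requires good correlation and agreement, not merely a non-significant t-test. But it sets no acceptable limit and no restriction by group.

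**Conclusion.** The concern holds as a gap in the specified analysis: three distinct groups are enrolled, and no by-group estimate or group term on the method difference is planned. It should be corrected, because a near-zero pooled bias could be reported that describes none of the groups.

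The cancellation of opposite biases holds whatever the SD. The power figures do not: they rest on an assumed SD of differences of 36% and on assumed biases. For 0/+15/-15% the group test's power runs from above 0.99 to 0.55 over SDs of 18% to 51%.

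Two stronger readings should be avoided. A reader might infer that the limits of agreement average out too; they widen, in that case from ±70.6 to ±74.5 points. A reader might also infer that a group test would reliably expose any important difference. At SD 36% it would miss a 10% bias confined to one group about four times in five.

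**What to change.** Add to DATA ANALYSIS, Study 1, for each ultrasound method to which Bland-Altman analysis applies:

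1. Mean bias with 95% CI, and limits of agreement, within each of the three groups, alongside the pooled values.
2. A regression (or one-way ANOVA) of the paired difference on group, reported as estimated differences between groups with 95% CIs.
3. A rule for conclusions: any statement about a group rests on that group's own bias CI and limits; a non-significant group test is not evidence that the groups agree; and the conclusion that ultrasound can replace fluoroscopy is limited to groups whose own estimates support it.
4. A sentence stating that the per-group results are estimation, not powered tests.

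The cost is a few lines of text and little extra analysis. Group is already an inclusion criterion, so no further participants, radiation or data are needed. The downside is precision: about ±13 points for bias in one group against ±7 pooled at SD 36%, so a group estimate near zero would not exclude the 10% bias that the study targets. Powering each group for 10% at that SD would take 102 to 104 per group, 306 to 312 in all, and is not proposed here.

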## STUDY 2:

In study 2, only lung function examination and ultrasound examination are carried out. These are made

Lung cancer: 1) the day before surgery, 2) 3 days after surgery and 3) 2 weeks after surgery.

Oesophageal cancer: 1) the day before surgery, 2) 3 days after surgery and 3) 10 days after surgery (after which most are discharged).

LVAD implantation: 1) the day before surgery, 2) 14 days after surgery and 3) 3 months after surgery.

Heart transplant: 1) in close relation to the write-up on the heart transplant list, 2) 14 days after the operation and 3) 3 months after the operation

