## ENDPOINTS

#### STUDY 1:

Diaphragm movement and thickening fraction compared to the cranial movement of the diaphragm as measured by translucency (gold standard) for the following measures:

Primary endpoint:

• Movement of the right hemidiaphragm: 1. M-mode method.

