## Secondary endpoints

- o Movement of the right hemidiaphragm by 1. Area method & 2. B-mode.
- Thickening fraction of the right hemidiaphragm: 1. B-mode.
- o Inspiratory pressure

The above is assessed by correlations and Bland-Altman analysis where relevant.

Correlations are made between lung function (FEV1, FVC, FRC) and ultrasound measurement of diaphragm function (see above) as well as diaphragm function measured by transillumination.

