#### Secondary endpoints

- Area method for diaphragm movement (ultrasound and transillumination for LVAD patients).
- B-mode method of diaphragm movement (ultrasound).
- Lung function (FEV1, FVC, FRC).

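### Study 1's zero-difference test is not limited to measures in the reference's unit, which leaves the Area method's test uninterpretable, and no interval is planned for the difference between ultrasound methods

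*Combined protocol and SAP*

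**What the plan says.** The analysis section for Study 1 sets the measurement scale with "Movement is measured continuously (centimeters or square centimeters". It then states that "The different measurement methods are compared individually with the golden standard with the paired T-test", with Wilcoxon's test as the fallback, and adds: "The 0 hypothesis is that there is no difference between the index method and the golden standard". A Bland-Altman plot and a correlation with the reference are also planned for each index test.

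The Area method is among the measures of movement. The ultrasound section says "Diaphragm movement is measured in 3 different ways: M-mode, Area method and B-mode", and the secondary endpoints for Study 1 list Area and B-mode movement, thickening fraction and inspiratory pressure. The reference is set in the Study 1 endpoints: "Diaphragm movement and thickening fraction compared to the cranial movement of the diaphragm as measured by translucency (gold standard". For the listed endpoints the plan adds "The above is assessed by correlations and Bland-Altman analysis where relevant".

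The Hypothesis/Aim section wants the precision of several ultrasound methods compared, with X-ray as the reference. The Perspective section for Study 1 expects the study to single out the best method.

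**The concern.** There are two separate gaps.

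**Units.** A paired test of zero mean difference has meaning only when both members of the pair are in the same unit. Cranial movement is a displacement, so it is a length, although no unit is printed for it. An area minus a length has no meaning, and the p-value would be reported as if it described the Area method's agreement with fluoroscopy.

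**Comparison between methods.** Every planned comparison sets one method against fluoroscopy. The MANOVA concerns sex, age and BMI, and the remaining correlations concern lung function. No contrast between ultrasound methods, ranking rule or criterion for the best method is given. Separate bias tests cannot fill that place, because at a given bias a noisier method is less likely to be flagged. A statement that one method is better than another would have no measure of uncertainty behind it.

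**Working it through.** **1. The plan's own figure.** The Study 1 strength calculation uses bias 10%, SD 36%, power 0.8 and alpha 0.05, and states 92 participants. The paired formula n = ((z_alpha + z_power) × SD / bias)² gives ((1.960 + 0.842) × 36 / 10)² = 101.7, so 102, or 104 with the exact t-test. The stated 92 is not reproduced. That is a separate matter, and this point does not depend on it. With 100 participants and an SD of differences of 36%, power at 10% bias is 0.785.

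**2. Units.** Suppose the area is exactly k times the fluoroscopic length x. The paired difference is (k − 1)x, so |t| = mean(x) / SD(x) × √n whatever the value of k (k ≠ 1). The strength calculation for Study 2 gives mean 6.65 and SD 2.38 for M-mode. Borrowing that ratio as an assumption for the reference, |t| = 6.65 / 2.38 × √100 = 27.9. A measure that tracks the reference perfectly would be rejected overwhelmingly. Its sign depends only on whether k is above or below 1. With k between 1 and 10, recording the length in millimetres instead of centimetres reverses it.

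**3. Is there an area reference?** The secondary endpoints for Study 2 include "Area method for diaphragm movement (ultrasound and transillumination for LVAD patients". That is a Study 2 endpoint. The Study 2 schedule says "In study 2, only lung function examination and ultrasound examination are carried out", and the section on transillumination confines it to Study 1. These passages conflict with each other and give Study 1 no reference in square centimetres.

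**4. What the bias test shows for like-unit methods.** If M-mode and fluoroscopy both have SD 36% and correlate at rho (assumed; the plan says it has no test-retest data), the SD of differences is 36 × √(2(1 − rho)), and the zero-bias limits of agreement are ±1.96 times that. Probabilities are from the noncentral t at n=100, two-sided 0.05.

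| rho (assumed) | SD of differences | Limits of agreement | Non-significant at 10% bias | Non-significant at 5% bias (assumed) |
|---|---|---|---|---|
| 0.5 | 36.0% | ±71% | 21% | 72% |
| 0.7 | 27.9% | ±55% | 6% | 57% |
| 0.8 | 22.8% | ±45% | 1% | 41% |
| 0.9 | 16.1% | ±32% | about 0% | 13% |

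At the plan's own 10% bias the test misses little unless rho is low. The large miss rates belong to smaller biases that the plan does not target. At an assumed 4% bias, the test is significant with probability 0.98, 0.51 and 0.17 for an SD of differences of 10%, 20% and 40%.

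**5. Is a comparison between methods feasible?** Simulation at n=100, with fluoroscopy and both methods normal with SD 36%, paired bootstrap 95% intervals, and a partial correlation of the two methods given fluoroscopy of 0 or 0.5. All correlations are assumed. Residual SD is 36 × √(1 − r²).

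| r with fluoroscopy | Power, SD of differences | Power, residual SD |
|---|---|---|
| 0.9 v 0.8 | 0.93 / 0.98 | 0.90 / 0.98 |
| 0.8 v 0.7 | 0.54 / 0.71 | 0.49 / 0.71 |

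For 0.9 v 0.8 the SDs of differences are 16.1 and 22.8 points, a gap of 6.7, with interval half-width 3.8 or 3.2 points. With equal r of 0.9 the false-positive rate is 0.06-0.07, so the intervals are slightly too narrow and the powers slightly flattering.

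**6. Why residual SD cannot stand alone.** A method that reads half the true movement with r = 0.92 has residual SD 36 × √(1 − 0.92²) = 14.1 and a bias of −50%. An unbiased method with r = 0.85 has 36 × √(1 − 0.85²) = 19.0. Ranking on residual SD would choose the first.

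**The case against.** The strongest case on the other side has four parts.

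- **The aim can be read more narrowly.** The aim, the Study 1 design statement and the lay summary can all be taken to mean each method against X-ray only, which is what the analysis delivers. The clearest sign of a comparison between methods is in the Perspective section, which is neither an objective nor an endpoint. This stands in part: the aim alone does not settle it. But it speaks of comparing precision across methods, and with the Perspective claim the narrow reading leaves a promised conclusion without an analysis.
- **Numbers, not only plots, will be available.** Bias, limits of agreement and correlations for M-mode and B-mode can be set side by side. This stands, so it would be wrong to infer that methods can be compared only by eye. What is missing is an interval for the difference.
- **Analyses are already qualified as applying where relevant.** The qualifier covers correlations and Bland-Altman, and does not expressly limit the paired test. For thickening fraction and inspiratory pressure it is unclear whether the paired test is meant at all, so one should not assert that it is.
- **An area might be read from the film.** Film clips are recorded, so this is possible. The Study 1 endpoints do not say so, and the criticism of the Area test is conditional on that.

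A reader might also infer that the plan treats a non-significant result as proof of agreement. No passage says this. The ethics section makes giving up fluoroscopy depend on good correlation and agreement, and Bland-Altman is planned.

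**Conclusion.** The point holds, within limits. As written, the paired test extends to a measure in square centimetres against a reference that is a length. Unless an area is taken from the film, the Area result says nothing about agreement. This concerns a secondary endpoint. It does not follow that Study 1's primary analysis is unsound: M-mode against fluoroscopy is length against length, the sample size is based on that bias, and the test is a valid test of bias for M-mode and B-mode.

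The missing comparison between methods is a real gap if the claim to identify the best method is kept. It is feasible at n=100, but only for clearly different methods. The unit argument needs no numerical assumption beyond the reference being a length. The power figures rest on assumed correlations and on the plan's SD of 36% applying to every method.

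**What to change.** Amend the Study 1 data analysis section as follows.

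1. Limit the paired test and the raw Bland-Altman analysis to M-mode and B-mode movement. Label the test as one of bias. Report mean bias and limits of agreement with 95% confidence intervals as the main result.
2. For the Area method and thickening fraction, regress fluoroscopic movement on the measure and report r and residual SD. Do the same for inspiratory pressure, reported separately because it is not an ultrasound measure. Alternatively, state in the Study 1 endpoints that an area is read from the fluoroscopy film; Area then joins item 1.
3. Report paired bootstrap 95% intervals for the M-mode v B-mode difference in bias and in SD of differences, and for differences in residual SD across the ultrasound methods. Show residual SD beside bias where bias is defined, and do not use it alone to name an optimal method. If this comparison is not wanted, drop the Perspective claim.

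The cost is wording and some computation on the same data, with no new measurements or participants. Two limits should be stated openly. Methods of similar quality will probably not be separated at n=100. Area and thickening fraction can be judged only after calibration, so their bias cannot be assessed.
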